5.2.5.2. Venetoclax and Azacitidine Dose Modifications and Delays Due to Nonhematologic Toxicity

Renal abnormalities ranging from elevated serum creatinine to renal failure have been reported with rare frequency in patients treated with azacitidine. In addition, renal tubular acidosis, defined as a decrease in serum bicarbonate to < 20 mmol/L in association with an alkaline urine and hypokalemia (serum potassium < 3 mmol/L), has been rarely observed. If unexplained reductions in serum bicarbonate (< 20 mmol/L) occur, the azacitidine dose should be reduced by 50% on the next cycle. Similarly, if unexplained elevations in serum creatinine or blood urea nitrogen to ≥ 2 -fold above baseline values and above the ULN occur, the next cycle should be delayed until values return to normal or baseline, and the azacitidine dose should be reduced by 50%. The reduced dose should be maintained during subsequent cycles unless toxicity develops.

For venetoclax-related or venetoclax/azacitidine-related nonhematologic toxicities that are \geq Grade 3 that do not resolve to \leq Grade 1 or baseline levels with adequate supportive care, venetoclax dosing should be held until resolution to \leq Grade 1 or baseline levels. While venetoclax is held, magrolimab and azacitidine treatment can be continued as scheduled.

For other azacitidine only-related nonhematologic toxicities or nonhematological toxicities that do not resolve after holding venetoclax that are \geq Grade 3 that do not resolve to \leq Grade 2 or baseline levels, azacitidine dosing should be delayed up to 14 days until resolution to \leq Grade 2 or baseline levels. If \geq Grade 3 toxicities continue despite this dose delay, dose modification of azacitidine should be performed in accordance with Table 10.

Table 10. Azacitidine Dose Modification for Nonhematologic Toxicities

	Azacitidine Dosing Instructions if Recovery ^a is Not Achieved Within 14 Days		
Toxicity	First Occurrenceb	Second Occurrenceb	Third Occurrenceb
	Reduce azacitidine dose to 50 mg/m ² administered Days 1–7 per cycle	Reduce azacitidine dose to 37.5 mg/m² administered Days 1–7 per cycle	Reduce azacitidine dose to 25 mg/m² administered Days 1–7 per cycle.
	AND	AND	AND
Grade 3 or higher nonhematologic adverse events that are clinically relevant	Reassess toxicity on subsequent cycle; if still persistent despite dose delay, proceed to second occurrence.	Reassess toxicity on subsequent cycle; if still persistent despite dose delay, proceed to third	Reassess toxicity on subsequent cycle; if still persistent despite dose delay, then administer azacitidine at 25 mg/m ² on Days 1–5 per cycle.
	second occurrence.	occurrence.	Reassess toxicity on subsequent cycle.
			Fourth occurrence and beyond: If toxicity still persists, then contact the medical monitor for azacitidine dosing instructions.

a Recovery is defined as improvement of nonhematologic toxicity to ≤ Grade 2 or baseline value within 14 days of dose delay

For Grade 3 or higher nonhematologic AEs that are clinically relevant and related to venetoclax, hold venetoclax until toxicity is resolved to Grade 2 or lower, or to baseline grade.

5.2.6. Prior and Concomitant Medications: Prohibited Concomitant Medications for Cohort 1

For the anti-leukemia regimens administered with magrolimab in this study, the current local or regional prescribing information should be consulted regarding permitted and prohibited concomitant medications.

Anti-leukemia therapies including chemotherapy (with the exception of hydroxyurea), targeted therapies, and immunotherapy are not permitted while patients are on study treatment.

Any investigational drugs other than magrolimab are prohibited during study treatment.

Concomitant use of venetoclax with strong CYP3A inducers or moderate CYP3A inducers should be avoided, as use with a strong CYP3A inducer decreases venetoclax C_{max} , which may decrease venetoclax efficacy.

Concomitant use of preparations containing St. John's wort is contraindicated during the study.

b Azacitidine may be dose-escalated back to the original dose or next higher dose level if there is resolution of the toxicity to

Section 2 or to baseline grade.

Conversely, concomitant use of strong and moderate CYP3A inhibitors with venetoclax increases exposure of venetoclax and therefore may increase the risk of venetoclax-related toxicity including TLS. Venetoclax dose modification based on concomitant use of a strong or moderate CYP3A inhibitor or P-gp inhibitor at initiation, during, or after the ramp-up phase, is described in Table 11. Resume the venetoclax dosage that was used prior to concomitant use of a strong or moderate CYP3A inhibitor or P-gp inhibitor 2 to 3 days after discontinuation of the inhibitor. Avoid grapefruit products, Seville oranges, and starfruit during treatment with venetoclax, as they contain inhibitors of CYP3A.

For additional information about drug interactions with venetoclax, refer to the local prescribing information.

Table 11. Management of Potential Venetoclax Interactions with CYP3A and P-gp Inhibitors

Co-administered Drug	Initiation and Ramp-up Phase	Steady Daily Dose (After Ramp-up Phase)	
Posaconazole	Day 1 – 10 mg venetoclax Day 2 – 20 mg venetoclax Day 3 – 50 mg venetoclax Day 4 – 70 mg venetoclax	Reduce venetoclax dose to 70 mg	
Other strong CYP3A inhibitor	Day 1 – 10 mg venetoclax Day 2 – 20 mg venetoclax Day 3 – 50 mg venetoclax Day 4 – 100 mg venetoclax	Reduce venetoclax dose to 100 mg	
Moderate CYP3A inhibitor	Paduae the wanteeley does by at least 500/		
P-gp inhibitor	Reduce the venetoclax dose by at least 50%		

CYP3A = cytochrome P450 enzyme 3A; P-gp = P-glycoprotein

5.3. Cohort 2 (R/R AML Mag+MEC)

The start of the cycle is the first day of MEC.

Information for magrolimab is provided in Section 5.1. Magrolimab infusion should be completed at least 1 hour before starting MEC chemotherapy if given on the same day.

5.3.1. Description and Handling of Mitoxantrone

5.3.1.1. Formulation

Information regarding the formulation of mitoxantrone can be found in the local prescribing information.

5.3.1.2. Packaging and Labeling

Study drug(s) to be distributed to centers in the US and other participating countries shall be labeled to meet applicable requirements of the US FDA, EU Guidelines to Good Manufacturing Practice, Annex 13 (Investigational Medicinal Products), and/or other local regulations.

5.3.1.3. Storage and Handling

Further information regarding storage and handling of mitoxantrone is available in the local prescribing information.

5.3.2. Description and Handling of Etoposide

5.3.2.1. Formulation

Information regarding the formulation of etoposide can be found in the local prescribing information.

5.3.2.2. Packaging and Labeling

Study drug(s) to be distributed to centers in the US and other participating countries shall be labeled to meet applicable requirements of the US FDA, EU Guidelines to Good Manufacturing Practice, Annex 13 (Investigational Medicinal Products), and/or other local regulations.

5.3.2.3. Storage and Handling

Further information regarding storage and handling of etoposide is available in the local prescribing information.

5.3.3. Description and Handling of Cytarabine

5.3.3.1. Formulation

Information regarding the formulation of cytarabine can be found in the local prescribing information.

5.3.3.2. Packaging and Labeling

Study drug(s) to be distributed to centers in the US and other participating countries shall be labeled to meet applicable requirements of the US FDA, EU Guidelines to Good Manufacturing Practice, Annex 13 (Investigational Medicinal Products), and/or other local regulations.

5.3.3.3. Storage and Handling

Further information regarding storage and handling of cytarabine is available in the local prescribing information.

5.3.4. Dosage and Administration of Mitoxantrone, Etoposide, and Cytarabine

The MEC dosing regimen for Safety Run-in Cohort 2 is presented in Table 2. The treatment schedule is provided in Appendix Table 7.

Magrolimab infusion should be completed at least 1 hour before starting MEC chemotherapy if given on the same day.

5.3.5. Premedication and Prophylaxis for Mitoxantrone, Etoposide, and Cytarabine

Premedications for mitoxantrone, etoposide, and cytarabine can be administered per local institutional guidelines.

5.3.6. Dose Modification and Delays for Mitoxantrone, Etoposide, and Cytarabine

MEC is a cytotoxic therapy and causes myelosuppression. Given that patients with AML will also be cytopenic as a result of their leukemia, dose modifications or delays of MEC should only occur if there is no evidence of leukemia, as defined by a bone marrow blast count of < 5% and absence of circulating peripheral blasts.

In the setting of absence of leukemic disease, treatment with MEC should be delayed in instances of ANC $< 500/\text{mm}^3$ or platelets $< 50,000/\text{mm}^3$ until recovery to an ANC $\ge 1000/\text{mm}^3$ or platelets $> 75,000/\text{mm}^3$ or ANC and platelet values equal to or above the patient's baseline values.

The individual components of the MEC regimen have distinct dose modification considerations and are detailed below

Mitoxantrone

Mitoxantrone clearance is reduced by hepatic impairment. Patients with total bilirubin > 3.5 mg/dL should reduce the dose of mitoxantrone by 50%. Mitoxantrone can be dosed at the full dose once total bilirubin is $\le 3.5 \text{ mg/dL}$.

Etoposide

Etoposide is renally metabolized and dose modifications should be made for impaired CLcr. If CLcr is 15 to 50 mL/min, administer 75% of the etoposide dose. If CLcr is < 15 mL/min, consider further dose reductions per institutional guidelines (ie, a 50% dose reduction).

Liver dysfunction may reduce the metabolism and increase the toxicity of etoposide; however, dose adjustment instructions are not provided in the US prescribing information (USPI). For patients with total bilirubin (predominantly direct) > 3 mg/dL or AST $> 5 \times$ ULN, administer 50% of the etoposide dose. Etoposide can be dosed at standard levels once total bilirubin is < 3 mg/dL or AST is $< 5 \times$ ULN.

Cytarabine

No dose adjustments are required for renal or hepatic impairment.

5.3.7. Prior and Concomitant Medications: Prohibited Concomitant Medications for Cohort 2

For the anti-leukemia regimens administered with magnolimab in this study, the current local or regional prescribing information should be consulted regarding permitted and prohibited concomitant medications.

Anti-leukemic therapies, including chemotherapy (with the exception of hydroxyurea), targeted therapies, and immunotherapy, are not permitted while patients are on study treatment.

Any investigational drugs other than magrolimab are prohibited during study treatment.

Drugs with cardiotoxic potential are prohibited during the study because of the potential cardiotoxicity with the use of mitoxantrone.

In patients receiving oral anticoagulant therapy, partial thromboplastin time (PTT) or international normalized ratio (INR) should be closely monitored and adjusted as needed with the addition and withdrawal of treatment with mitoxantrone and etoposide.

In patients treated with oral digoxin, monitor plasma digoxin levels during cytarabine treatment.

Gentamycin used against *Klebsiella pneumoniae* and 5-Fluorocytosine are contraindicated during cytarabine treatment.

Co-administration of antiepileptic drugs and etoposide injection can lead to decreased seizure control due to pharmacokinetic interactions between the drugs.

Concomitant phenytoin or phenobarbital therapy is associated with increased etoposide clearance and reduced efficacy, and other enzyme-inducing antiepileptic therapy may be associated with increased etoposide clearance and reduced efficacy.

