3.1.1.2. DLT Definition

All toxicities will be graded according to the NCI CTCAE Version 5.0. A DLT is defined as any Grade 4 or higher hematologic toxicity or Grade 3 or higher nonhematologic toxicity (that has worsened in severity from pretreatment baseline) during the 4-week DLT assessment period and is related to magrolimab or magrolimab combination.

The following are exceptions to the DLT definition and are NOT considered DLTs:

- Myelosuppression (Grade 4 neutropenia and thrombocytopenia) lasting no longer than 42 days from the start of study treatment for Cohorts 1 and 2, and no longer than 21 days from the start of study treatment for Cohort 3. Complications within the first 4 weeks that are associated with myelosuppression, such as fevers, infections, bleeding, and related hospitalizations, will also not be considered DLTs. However, Grade 4 neutropenia or thrombocytopenia lasting longer than 42 days from the start of study treatment for Cohorts 1 and 2, or 21 days from the start of study treatment for Cohort 3, without evidence of leukemia, will be considered DLTs. Absence of residual disease must be verified by peripheral blood count and bone marrow aspirate and biopsy at Day 43 (+ 10 days) for Cohorts 1 and 2.
- Grade 3 indirect/unconjugated hyperbilirubinemia that resolves to ≤ Grade 2 or pretreatment baseline with supportive care within 7 days and is not associated with other clinically significant consequences.
- Grade 3 isolated electrolyte laboratory abnormalities that resolve to ≤ Grade 2 or pretreatment baseline with supportive care within 7 days and are not associated with other clinically significant consequences.

- Grade 3 elevation in alanine aminotransferase (ALT), aspartate aminotransferase (AST), or alkaline phosphatase (ALP) that resolves to ≤ Grade 2 or pretreatment baseline with supportive care within 7 days and is not associated with other clinically significant consequences.
- Grade 3 nausea, vomiting, or diarrhea that resolves to ≤ Grade 2 or pretreatment baseline with supportive care within 7 days.
- Grade 3 fatigue that resolves to ≤ Grade 2 or pretreatment baseline within 2 weeks.
- Grade 3 magrolimab IRRs in the absence of an optimal pretreatment regimen, which is defined as acetaminophen or a comparable non-steroidal anti-inflammatory agent, plus an antihistamine and corticosteroids.

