a If patient achieved blast clearance after Cycle 1, one additional cycle of MEC will be given (total 2 cycles). If patient achieved blast clearance only after Cycle 2, a third cycle of MEC will be given. If no blast clearance at the end of Cycle 2, patient should be discontinued from the study.

Table 3. Dose Level and Schedule for Safety Run-in Cohort 3 (Post-Chemo Maint Mag+CC-486)

	Dose Sched	Dose Schedule (Day per 28-Day Cycle)		
Drug/Dose/Route	Cycle 1	Cycle 2	Cycle 3+	
CC-486 300 mg PO	Days 1-14	Days 1-14	Days 1-14	
	Magrolimab Administration			
Magrolimab 1 mg/kg IV (over 3 hours)		Days 1, 4		
Magrolimab 15 mg/kg IV (over 3 hours)		Day 8		
Magrolimab 30 mg/kg IV (over 2 hours)	Days 11 an	Days 11 and 15, and then QW × 5 doses		
Magrolimab 30 mg/kg IV (over 2 hours)	Q2W beginning 1 we	Q2W beginning 1 week after the 5th weekly 30 mg/kg dose		

IV = intravenous; PO = orally; Q2W= every 2 weeks; QW = once weekly

Table 4. Dose De-escalation for Safety Run-in Cohort 1 (1L Unfit AML Mag+Ven+Aza)

Dose Level	Dosing (28-Day Cycle)	
Venetoclax starting dose	Cycle 1: 100 mg PO Day 1, 200 mg Day 2, 400 mg Days 3-28, Cycle 2 and later: 400 mg Days 1-28	
Level Minus 1	Cycle 1: 100 mg PO Day 1, 200 mg Day 2, 400 mg Days 3-21, Cycle 2 and later: 400 mg Days 1-21	
Level Minus 2	Cycle 1: 100 mg PO Day 1, 200 mg Day 2, 400 mg Days 3-14, Cycle 2 and later: 400 mg Days 1-14	
Magrolimab and azacitidine (all dose levels)	Will be administered at the starting dose and not dose-reduced for any of the dose minus levels	

PO = orally

Table 5. Dose De-escalation for Safety Run-in Cohort 2 (R/R AML Mag+MEC)

	Dosing (28-Day Cycle)		
	MEC Magrolimab		
Dose Level	Cycles 1 and 2 to 3 ^a	Up to 12 Months	
Starting dose	Mitoxantrone 8 mg/m ² IV (over 15-30 min) Days 1-5 Etoposide 100 mg/m ² IV (over 30-60 min) Days 1-5 Cytarabine 1000 mg/m ² IV (over 1 hour) Days 1-5	Magrolimab: 1 mg/kg IV (over 3 hours) Days 1, 4; 15 mg/kg IV (over 3 hours) Day 8; 30 mg/kg IV (over 2 hours) Days 11 and 15, and then QW × 5 doses 30 mg/kg IV (over 2 hours) Q2W beginning 1 week after the 5th weekly 30 mg/kg dose	

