5.2.5.1. Venetoclax and Azacitidine Dose Modifications and Delays Due to Hematologic Toxicity

Dose modifications and delays for venetoclax due to AEs should follow Table 9 or the venetoclax local prescribing information. If bone marrow assessment done in Cycle 1 shows blast clearance (< 5%), venetoclax dose for the remainder of the cycle can be omitted to allow for count recovery.

Table 9. Venetoclax and Azacitidine Dose Modifications and Delays Due to Hematological Toxicity

Event	Occurrence	Action Taken ^a	
Grade 4 neutropenia with or without fever or infection; or Grade 4 thrombocytopenia	Occurrence prior to achieving remission ^b	In most instances, venetoclax and azacitidine cycles should not be interrupted due to cytopenia prior to achieving remission.	
	First occurrence after achieving remission and lasting at least 7 days ^{c,d}	Delay subsequent treatment cycle of venetoclax and azacitidine and monitor blood counts. Once the toxicity has resolved to Grade 1 or 2, resume venetoclax therapy at the same dose and decrease the duration to 21 days. Resume azacitidine at the same dose.	
	Second occurrence in cycles after achieving remission and lasting 7 days or longer	Delay subsequent treatment cycle of venetoclax and azacitidine and monitor blood counts. Once the toxicity has resolved to Grade 1 or 2, resume venetoclax therapy at the same dose and same duration (21 days). Resume azacitidine at the same dose.	
	Third occurrence in cycles after achieving remission and lasting 7 days or longer	Delay subsequent treatment cycle of venetoclax and azacitidine and monitor blood counts. Once the toxicit has resolved to Grade 1 or 2, resume venetoclax therap at the same dose and decrease the duration to 14 days. Resume azacitidine at the same dose.	
	Fourth occurrence in cycles after achieving remission and lasting 7 days or longer	Delay subsequent treatment cycle of venetoclax and azacitidine and monitor blood counts. Once the toxicity has resolved to Grade 1 or 2, resume venetoclax therapy at the same dose and duration (14 days) and reduce the azacitidine dose to 50 mg/m².	
	Fifth occurrence in cycles after achieving remission and lasting 7 days or longer	Delay subsequent treatment cycle of venetoclax and azacitidine and monitor blood counts. Once the toxicity has resolved to Grade 1 or 2, resume venetoclax therapy at the same dose, decrease the duration to 7 days, and continue the azacitidine dose at 50 mg/m².	

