- 1 In the absence of count recovery at Day 28, CBC should be collected weekly for 2 weeks or until start of the next cycle, whichever is earlier. The best CBC result within the ±2-week window is to be used for the response assessment, with the date of response being the date of the bone marrow assessment. Complete blood count does not need to be repeated if the prior CBC (including prior Day 28 CBC) is within 3 days of Day 1.
- m Peripheral blood smears for blasts are to be collected along with bone marrow aspirate/biopsy and assessed locally.
- n Peripheral blood smears for general morphology will be collected predose and assessed locally.

Appendix Table 4. Magrolimab Administration and Associated Assessment Schedule – Treatment Period for All Cohorts

Visit Window (Days)		Nonea			± 3ª		Weekly x 5	Every 2 weeks
Day	1	2	4	8	11	15	± 3 days	± 3 days
Vital signs ^b			X	X	X	X	X	
Hemoglobin ^c								
Peripheral blood sample for receptor occupancy ^{d,e}	Within 72 hours prior to magrolimab	X		Within 12 hours prior to magrolimab			Within 12 hours prior to magrolimab dosing for 2nd	Within 12 hours prior to magrolimab dosing before 1st,
Pharmacokinetic	dosing			dosing			weekly dose	5th, 9th, 15th and 21st biweekly
Antidrug antibodies ^f								maintenance doses of 30 mg/kg
Magrolimab Administration								
Premedicationg	X		X	X	X			
Magrolimab ^h	X		X	X	X	X	X	X

CBC = complete blood count; PK = pharmacokinetic(s)

- a In cases of magrolimab repriming/re-escalation following a treatment delay (Section 5.1.3), follow magrolimab schedule of assessment and administration for repriming (Appendix Table 5).
- b Vital signs will be assessed prior to administration of magrolimab. Details are provided in Section 6.5.4.
- c Hemoglobin must be performed within 24 hours prior to magrolimab dosing on Days 1 and 4 to ensure hemoglobin is ≥ 9 g/dL. Within 24 hours prior to each of the first 2 doses of magrolimab infusion during initial treatment, all patients must have a documented hemoglobin ≥ 9 g/dL. Patients who do not meet these criteria must be transfused and have their hemoglobin rechecked to meet 9 g/dL prior to each of the first 2 doses of magrolimab. An additional hemoglobin check must be performed 3 to 6 hours after the initiation of the first 2 doses of magrolimab (see Section 5.1.2).
- d Samples will be collected predose within 12 hours prior to administration of magrolimab.
- e Samples for receptor occupancy will be collected at selected study sites.

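### In 5.3.6 the MEC delay and etoposide hepatic rules use *or* in both trigger and recovery, so the text contradicts itself when both values triggered and only one recovers

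*Protocol*

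**What the plan says.** All the dosing text is in Protocol 5.3.6.

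- **MEC delay.** "In the setting of absence of leukemic disease, treatment with MEC should be delayed in instances of ANC" is below 500/mm³ or platelets are below 50,000/mm³. The delay lasts until ANC is at least 1000/mm³ or platelets exceed 75,000/mm³, "or ANC and platelet values equal to or above the" patient's own baseline. The rule applies only with marrow blasts below 5% and no circulating blasts.
- **Etoposide reduction.** "For patients with total bilirubin (predominantly direct) > 3 mg/dL or AST" above 5 × ULN, half the dose is given.
- **Etoposide restoration.** "Etoposide can be dosed at standard levels once total bilirubin is < 3 mg/dL or AST is" below 5 × ULN.
- **Mitoxantrone, for comparison.** The dose is halved at bilirubin above 3.5 mg/dL and restored at 3.5 mg/dL or less, so trigger and release are exact complements.

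Three other places bear on when the MEC rule is used. Table 2, footnote a: "If patient achieved blast clearance after Cycle 1, one additional cycle of MEC will be given (total 2 cycles"). Appendix Table 3, footnote l, plans for unrecovered counts: "In the absence of count recovery at Day 28, CBC should be collected weekly for 2 weeks or until start of the next cycle". The DLT definition (3.1.1.2) tolerates "Myelosuppression (Grade 4 neutropenia and thrombocytopenia) lasting no longer than 42 days from the start of study treatment for Cohorts 1 and 2".

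**The concern.** If either of two abnormal values is enough to start a delay or reduction, the release has to clear every value that started it. Here *or* stands on both sides. Once both values have triggered, recovery of one satisfies the release clause while the other still satisfies the trigger clause. Two sites following the same section could then act in opposite ways.

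The wording nearby suggests a drafting slip. The baseline route in the same MEC sentence uses *and* for the two counts. As written, a patient recovering to baseline needs both counts, and a patient recovering to the absolute cut-offs needs only one. Table 9 (Cohort 1) also has a two-lineage *or* trigger but ties resumption to the toxicity itself: "Once the toxicity has resolved to Grade 1 or 2, resume venetoclax therapy at the same dose". That contrast is modest, because Table 9 does not spell out both lineages either.

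What is at stake is patient safety in Cohort 2, the one cohort still open: a further myelosuppressive cycle with one lineage still below its delay threshold, or full-dose etoposide with one liver value still beyond its limit. The protocol says the US label gives no hepatic adjustment for etoposide, so this sentence is the operative rule.

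**Working it through.** The plan gives no figure on this point, so there is none to reproduce. The check is whether trigger and release can both be true for the same values.

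**MEC.** Inputs from 5.3.6: trigger T = (ANC < 500 or platelets < 50,000); release R = (ANC ≥ 1000 or platelets > 75,000) or (both counts at or above baseline). Assume both counts triggered, and at recheck at least one is below baseline, so the baseline route is not met. One test value per band gives 3 × 3 = 9 combinations. The last column is the rule proposed under the fix.

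| ANC | Platelets | T still true | R true as written | Proposed rule releases |
|---|---|---|---|---|
| 200 | 30,000 | yes | no | no |
| 200 | 60,000 | yes | no | no |
| 200 | 80,000 | **yes** | **yes** | no |
| 700 | 30,000 | yes | no | no |
| 700 | 60,000 | no | no | no |
| 700 | 80,000 | no | yes | no |
| 1200 | 30,000 | **yes** | **yes** | no |
| 1200 | 60,000 | no | yes | no |
| 1200 | 80,000 | no | yes | yes |

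As written, R is true in 5 of 9, and in 2 of those 5 T is true as well. Under the proposed rule release occurs in 1 of 9 and T is true in 0 of those.

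*Dependence on baseline.* At ANC 300 and platelets 80,000 with baseline 2000 and 200,000, T and R are both true: a contradiction. With the same counts and baseline 200 and 10,000, the baseline route is met and the patient is released under the present text and under the fix alike. That is the intended exception.

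*Why not a plain* and. If only ANC triggered and the patient reaches ANC 1500 with platelets 60,000, a plain *and* would hold MEC for a lineage that never fell below 50,000. The proposed rule releases.

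**Etoposide.** T = (predominantly direct bilirubin > 3 mg/dL or AST > 5 × ULN); R = (bilirubin < 3 or AST < 5 × ULN).

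| Bilirubin (mg/dL) | AST (× ULN) | T | R as written | Both ≤ limits |
|---|---|---|---|---|
| 2.5 | 2 | no | yes | yes |
| 2.5 | 8 | **yes** | **yes** | no |
| 4.0 | 2 | **yes** | **yes** | no |
| 4.0 | 8 | yes | no | no |

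T and R are both true in 2 of 4. Requiring both values to be within limits leaves 0.

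*Equality.* On bilirubin 2, 3, 5 by AST 1, 5, 6 (9 combinations), the present text reduces in 5, restores in 5, does both in 2 and neither in 1 (bilirubin 3, AST 5): 5 + 5 − 2 + 1 = 9. With *and* and strict <, 3 combinations fall under neither rule; with *and* and ≤, none does.

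**When it could arise.** The MEC rule needs leukemia to be absent, and patients with blast clearance are the ones given a further cycle. Section 3.3 gives that cycle to responders, including MLFS, which under Appendix 7 needs no hematologic recovery. The DLT tolerance to Day 42 runs 42 − 28 = 14 days past one cycle. For etoposide, inclusion criterion 3 requires AST ≤ 3 × ULN and bilirubin ≤ 1.5 × ULN (≤ 3 × ULN only with Gilbert syndrome and primarily unconjugated). With 2 to 3 MEC cycles planned, the rule matters mainly at the 1 or 2 later ones.

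**The case against.** The strongest reply is that the conservative instruction never lapses. The trigger sentences carry no exception: a patient at ANC 200 and platelets 80,000 is still one in whom MEC should be delayed, and at direct bilirubin 5 mg/dL half-dose etoposide is still called for whatever AST does. The etoposide trigger is an instruction, while restoration is only permitted. This stands, and it means the text contradicts itself rather than cleanly releasing the dose.

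A second reply is that both sentences list the same items in the same order, so an item-by-item reading is natural. It would resolve the conflict, but the text does not state it and no other section requires both values to recover.

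Other safeguards also stand. Section 7.7 asks for discontinuation to be considered when ALT or AST is ≥ 3 × ULN with bilirubin > 2 × ULN, no cholestasis and no other explanation. A starting point of bilirubin 5 mg/dL and AST 6 × ULN meets both numeric limits for any bilirubin ULN below 2.5 mg/dL (assumed; the protocol gives no ULN). At bilirubin 5, mitoxantrone also stays halved. Sections 7.8.4 to 7.8.6 restrict MEC to physicians experienced with AML.

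Two stronger readings are tempting. A reader might infer that the rules are void from the start when only one value triggered, because the other already meets the release. The references to recovery point back to the value that was abnormal, so the documents do not support that. A reader might also infer from the DLT exception that both counts low is the expected state when the next cycle is due. The exception says what is tolerated, not how often it happens, and footnote l only schedules blood counts.

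**Conclusion.** Wrong as written. Each rule gives two incompatible instructions when both values triggered and one has recovered. For MEC this covers 2 of 9 band combinations, given that at least one count is still below baseline; for etoposide it covers 2 of 4. These count value combinations over chosen bands. A reader might take them as the share of patients affected, but the protocol gives no such frequency, and patients whose counts were already low at baseline may be released properly by the baseline route.

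The MEC case is the more relevant one, since it can arise in patients with blast clearance who are due a further cycle. The etoposide case has small reach, given the entry limits, section 7.7 and the few later cycles. Nothing here touches the sample size or the primary analysis.

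**What to change.** Amend two sentences in 5.3.6.

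- **MEC.** Resume once every count that prompted the delay has recovered (ANC ≥ 1000/mm³ if ANC was below 500; platelets > 75,000/mm³ if platelets were below 50,000) and neither count is below its delay threshold, or once both counts are at or above baseline. The middle clause largely restates the existing trigger; stating it removes the contradiction. The baseline route is kept as it is.
- **Etoposide.** Give the standard dose only when neither reduction criterion is met: total bilirubin (predominantly direct) ≤ 3 mg/dL and AST ≤ 5 × ULN. Keeping the qualifier stops unconjugated hyperbilirubinemia from holding the dose down, and moving from < to ≤ closes the gap at exact equality.

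The cost is a short amendment and somewhat longer MEC delays or etoposide reductions in some patients, including responders awaiting a further cycle. The protocol gives no basis for saying how many. A lineage that never fell below its delay threshold would not hold up MEC.
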